birth may be a self-limiting disorder and therefore a benign condition, it remains difficult to identify infants in need for further respiratory support at the NICU. Admission to the NICU not only causes parental stress but also contributes to additional healthcare costs. (Pierro *et al.*, 2023). Using the lung ultrasound score for the early identification of neonates in need of respiratory support persisting more than 1 hour would be highly advantageous. Neonates requiring further treatment could benefit from early admission at the NICU, whilst the others could be prevented from an ‘unnecessary’ transfer to the NICU which would in turn reduce the burden of transport, workload, and healthcare costs.

3. Objectives

The objective of this study is to evaluate the role of NPLUS during the immediate transition after birth of late preterm and full-term neonates using the lung ultrasound score to predict the need for respiratory support persisting more than 1 hour. NPLUS will be conducted at specific time points after birth (at 5, 15, 30 and 60 minutes) by a trained medical doctor who will complement as an additional member of the medical team.

- **Hypothesis I:**

We hypothesize that there is a cut-off value of the lung ultrasound score performed 5, 15, 30 and 60 minutes after birth that is reliable to predict the need for respiratory support persisting > 1 hour in late preterm and full-term neonates.

- **Hypothesis II:**

We hypothesize that there is a cut-off value of the lung ultrasound score performed 5, 15, 30 and 60 minutes after birth that is reliable to predict the need for admission to the NICU in late preterm and full-term neonates.

- **Hypothesis III:**

We hypothesize that neonates in need of respiratory support persisting > 1 hour have significantly higher lung ultrasound scores even when assessed already in 5, 15, 30 and 60 minutes after birth, compared to neonates requiring respiratory support < 1 hour after birth.

- **Hypothesis IV:**

We hypothesize that there is a correlation between the lung ultrasound score performed at 5, 15, 30, and 60 minutes after birth, the length of respiratory support and the required mode of ventilation.

- **Hypothesis V:**

We hypothesize that the lung ultrasound score assessed by NPLUS decreases between 5 and 60 minutes after birth.

4. Design, setting and participants

The present **study design** is conceived as an observational prospective pilot study.

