NPLUS is conducted with a 12-15 MHz linear transducer preferably using the presets "lung" or "small parts". Sequences of 3-5 seconds are saved and scored. To minimize interference with the routine care, NPLUS will be performed by an independent trained medical doctor and clinical findings will not be passed on to the medical team in charge. The only exception to communicate the obtained NPLUS findings would be a pneumothorax. In this situation the diagnosis will be communicated to the medical team, and the neonate will be excluded from the study.

To ensure **inter-observer reliability** the anonymous video sequences are then blinded and rated by two independent neonatologists.

Inclusion criteria:

- Late preterm neonates (born between 34 0/7 and 36 6/7 weeks of gestation) and full-term neonates (born later than 36 6/7 weeks of gestation) delivered by Caesarean section at the Department of Obstetrics and Gynaecology, Medical University of Graz
- Presence of any sign of respiratory distress (defined as tachypnoea/ dyspnoea, grunting, flaring of the nostrils or chest retractions)
- Written informed consent obtained from the parents prior to birth.

Exclusion criteria:

- Presence of cardiopulmonary malformations
- Patients with pneumothorax diagnosed by NPLUS

Sample size: Statistical analysis for cut-off determination will be performed with a sample-size of 40 individuals, excluding patients with pneumothorax diagnosed by NPLUS. Hence, we aim at comparing 20 neonates who are transferred to the NICU with 20 neonates who initially need respiratory support but then do not require any 60 minutes after birth.

Sample size calculations cannot be performed beforehand, since no data from previous studies are available. Hence, this pilot study is conducted to generate data for the sample size calculation of the consecutive main study (Thabane *et al.*, 2010).

5. Statistical analysis

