Demographic information, clinical characteristics, and lung ultrasound features will be summarized. First, the Kolmogorov–Smirnov test will be applied to test the data significance, which will then be represented as the mean (standard deviation, SD) or median (interquartile range, IQR). The predictive performance of the lung ultrasound score for the need for respiratory support persisting more than 1 hour after birth and for admission to the NICU will be analysed by plotting the receiver operating characteristic (ROC) curve, and areas under the ROC curves (AUCs) determining cut-off values. Group differences in primary and secondary outcome parameters between patients who are transferred to the NICU in need for respiratory support for more than 60 minutes and patients who do not need any respiratory support after 60 minutes after birth are calculated using χ^2 and Fisher's exact tests for discrete variables, and t-test or Mann-Whitney U test for continuous variables. Additionally, the correlations between the lung ultrasound score, length of respiratory support and the mode of ventilation will be analysed using either the Spearman's rank correlation coefficient or the Pearson's correlation depending on which one is more appropriate. The correlation analyses are considered in an explorative sense; therefore, no multiple testing corrections will be performed. SPSS23.0 (IBM Corporation, New York, NY, USA) is used for statistical analysis.

6. Outcome measures

Primary

- Determination of the lung ultrasound score according to Rodriguez-Fanjul *et al.* 2020 at 5, 15, 30 and 60 minutes after birth
- Need for respiratory support persisting more than 1 hour
- Admission to the NICU

Secondary

- Length of respiratory support (in minutes)
- Mode of respiratory support (non-invasive versus invasive ventilation)
- Routinely obtained capillary blood gas analysis of the newborn
- Routinely obtained monitoring parameters including arterial oxygen saturation (SpO₂), heart rate (either by pulse oximetry or electrocardiography), and cerebral oxygen saturation (near-infrared spectroscopy)
- SpO₂/FiO₂ ratio (S/F ratio)
- pH of the umbilical artery
- Apgar score
- Pregnancy risk factors including intra-amniotic infection, and premature rupture of the membranes
- Prenatal corticosteroids

7. Research plan and time table

The study will start in spring 2024.

The study is designed for an approximate running time of three years.

8. References

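### Cut-offs are derived and judged in the same 40 infants without confidence intervals or internal validation, so any accuracy quoted at a data-chosen cut-off would be imprecise and, on average, optimistic

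*Combined protocol and SAP*

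**What the plan says.** Hypotheses I and II (section 3) each state that "there is a cut-off value of the lung ultrasound score performed 5, 15, 30 and 60 minutes after birth that is reliable" for predicting, respectively, support beyond one hour and NICU admission. The Background (section 2) gives the intended use: "Neonates requiring further treatment could benefit from early admission at the NICU", while other infants would be spared a transfer.

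Under Sample size in section 4, "Statistical analysis for cut-off determination will be performed with a sample-size of 40 individuals", made up of "20 neonates who are transferred to the NICU with 20 neonates who initially need respiratory support" but none at 60 minutes. The same paragraph says no calculation was possible and that "this pilot study is conducted to generate data for the sample size calculation of the consecutive main study".

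Section 5 covers "The predictive performance of the lung ultrasound score for the need for respiratory support persisting more than 1 hour after birth", and for NICU admission, by "plotting the receiver operating characteristic (ROC) curve, and areas under the ROC curves (AUCs) determining cut-off values". It does not say how a cut-off will be picked from the curve. Neither section 5 nor any other section mentions a confidence interval, bootstrap, cross-validation, split sample or validation cohort. The threshold of 8 mentioned in the Background describes a cited surfactant trial and is not adopted here. The statement in section 5 that results are explorative is attached to the correlation analyses only.

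**The concern.** A cut-off chosen because it separates these 40 infants well will, on average, separate them better than it separates new infants. Accuracy computed at that cut-off in the same infants inherits the advantage. Without intervals, the reader also cannot see how loosely 20 infants per group pin down the AUC, the accuracy at the cut-off, or the cut-off itself.

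A usable cut-off is the deliverable of Hypotheses I and II, so it and its apparent accuracy are what readers would take away, possibly to inform who goes early to the NICU. The main study's sample size would be affected by the optimism only if it were based on accuracy at the cut-off.

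**Working it through.** **Inputs from the document.** Two groups of 20; a score from 0 to 18 (section 2, adopted in section 4), giving 18 possible integer cut-offs; four time points; two outcomes. The only planned figure that can be reproduced is 20 + 20 = 40. No alpha, power, effect size or target precision is stated.

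**Assumptions not in the document.** True AUC 0.70, 0.75, 0.80, 0.85 or 0.90. Score is a rounded normal clipped to 0-18, with control mean/SD of 7/3, 5/2 or 6/4. This gives 15 settings per cut-off rule, each with 40,000 simulated studies.

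**Step 1: precision at 20 per group.**
- Wilson interval: [p + z²/2n ± z√(p(1−p)/n + z²/4n²)] / (1 + z²/n). For 15/20, the centre is (0.75 + 0.096)/1.192 = 0.710 and the half-width 0.178, giving 0.53-0.89. For 18/20 it gives 0.70-0.97.
- Hanley-McNeil standard error at AUC A = 0.75: Q1 = A/(2−A) = 0.600 and Q2 = 2A²/(1+A) = 0.643. The variance is [0.1875 + 19(0.600−0.5625) + 19(0.643−0.5625)]/400 = 0.00607, so SE = 0.078 and 1.96 × 0.078 = ±0.15.

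**Step 2: optimism.** In each simulated study the cut-off was chosen by the rule. Apparent accuracy was then compared with true accuracy at that same cut-off.

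| Rule | Sensitivity, apparent − true | Specificity, apparent − true |
|---|---|---|
| Youden | +0.033 to +0.059 | +0.037 to +0.065 |
| Closest to corner | +0.023 to +0.039 | +0.024 to +0.043 |
| Sensitivity at least 90% | +0.031 to +0.038 | −0.001 to +0.001 |
| Specificity at least 90% | −0.001 to +0.001 | +0.031 to +0.037 |

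Worked case: Youden, AUC 0.75, mean 7, SD 3, ties to the lower cut-off. Sensitivity is 0.754 apparent against 0.703 true (gap 0.051). Specificity is 0.686 against 0.630 (gap 0.056). The levels depend on how ties are broken, but the gaps do not, so the gaps are the figures to carry forward.

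**Step 3: stability of the cut-off.** At AUC 0.75, the middle 95% of Youden cut-offs ran from 6 to 11 at SD 3, from 4 to 8 at SD 2, and from 4 to 12 at SD 4.

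**Step 4: does the remedy work at this size?** Bootstrap correction (300 resamples, 2,000 simulated studies, mean 7, SD 3):

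| Setting | Measure | Apparent | Corrected | True |
|---|---|---|---|---|
| AUC 0.75, Youden | sensitivity | 0.752 | 0.715 | 0.701 |
| AUC 0.75, Youden | specificity | 0.685 | 0.643 | 0.632 |
| AUC 0.90, Youden | sensitivity | 0.862 | 0.836 | 0.827 |
| AUC 0.90, Youden | specificity | 0.824 | 0.791 | 0.778 |
| AUC 0.75, sensitivity at least 90% | sensitivity | 0.923 | 0.889 | 0.887 |
| AUC 0.75, sensitivity at least 90% | specificity | 0.377 | 0.377 | 0.380 |

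Under Youden at AUC 0.75 the correction removes (0.752−0.715)/(0.752−0.701) = 73% of the optimism in sensitivity and (0.685−0.643)/(0.685−0.632) = 79% in specificity. Under the fixed-sensitivity rule it removes (0.923−0.889)/(0.923−0.887) = 94% of the optimism in sensitivity.

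**The case against.** The strongest reply has four parts.

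1. *Section 5 names ROC curves, AUCs and cut-offs, and never promises sensitivity or specificity.* This is correct, and the optimism finding is therefore conditional. But the AUC describes no single cut-off, so calling a cut-off reliable needs some accuracy measure at it. The missing intervals matter whichever measures are reported.

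2. *This is a pilot, and deriving a provisional cut-off is a legitimate pilot aim.* This lowers the stakes. It does not correct the figures, and no section says the main study will validate the cut-off; the stated link is to its sample size.

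3. *The bias is small beside the noise, and correcting it gains little in a single study.* Largely true. Under Youden the root mean squared error of sensitivity falls only from 0.102 to 0.094 at AUC 0.75, and from 0.082 to 0.081 at AUC 0.90. For the Youden index at AUC 0.75 the gain is somewhat larger, from 0.155 to 0.132. The optimism is also an average: in about 14-23% of simulated samples the apparent Youden index did not exceed its true value. Intervals are therefore the more important half of the fix, and correction is a cheap addition.

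4. *Examining four time points is deliberate.* Agreed. A reader might infer that the best time point will be picked and its accuracy quoted. The document does not say so, and reporting all four involves no selection between them. Had it been planned, the optimism in the Youden index would rise to about 0.16-0.20 at true AUCs of 0.70-0.90 (assumed correlation between times about 0.6, control mean 6, SD 3.5), against about 0.09-0.12 for one time point in the same model.

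**Conclusion.** The point holds with its limits stated. The plan derives cut-offs and judges prediction in the same 20 against 20 infants, with no intervals, validation step or cut-off rule, while its hypotheses claim reliability. That much is plain from the text. The size is conditional on sensitivity and specificity being reported and on the assumed AUCs and score distributions: about 3-6 points on each under Youden, 2-4 under closest-to-corner, and 3-4 on the targeted measure alone under a fixed-sensitivity or fixed-specificity rule. Sampling error exceeds all of these.

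Three stronger readings go beyond the document:
- **The AUC is inflated.** At a time point fixed in advance nothing is fitted, so it is only imprecise.
- **Sensitivity and specificity are both inflated whatever the rule.** The rule is not stated, and a fixed-target rule leaves the other measure essentially unbiased.
- **The main-study sample size is compromised.** Section 4 does not say which pilot quantity will be used. If it is the AUC at a fixed time or the score SD, this bias does not enter.

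The change is worth making before the data are examined. It is an improvement to reporting and does not invalidate the pilot.

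**What to change.** Amend section 5 to:

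1. State the cut-off rule before the data are examined.
2. At all four time points, report 95% confidence intervals for the AUC and for sensitivity and specificity at the cut-off, and a bootstrap interval for the cut-off itself.
3. Repeat the whole cut-off selection in bootstrap resamples (for example 1,000) and give optimism-corrected sensitivity and specificity beside the apparent values. Intervals for the corrected values should come from the bootstrap, since an ordinary binomial formula does not apply to them. Include the choice of time point in the resampling only if one is selected from the data.
4. Describe the cut-offs as provisional pending validation in new infants.
5. If accuracy at the cut-off is used to size the main study, use the corrected values with their intervals.

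Cost: a few lines of text and a short script, possibly outside SPSS 23.0, the only package named. The bootstrap intervals for the corrected values are the most laborious part. No new infants or examinations are needed. The reported accuracy will look slightly less favourable, and under a Youden rule the correction is incomplete at this sample size.

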There is emerging evidence that NPLUS is a reliable tool to differentiate between the different causes leading to RDS in neonates. By today, different scoring systems have been developed in different clinical contexts. (Brat *et al.*, 2015; Mongodi *et al.*, 2021; Rodriguez-Gonzalez *et al.*, 2022) These scores aim at giving a comprehensive look on the lung's condition by screening the lung fields.

Despite the growing body of evidence, studies on NPLUS during stabilization and resuscitation immediately after birth are still scarce. In the study performed by Blank *et al.*, they found that in healthy term and late preterm infants within the first 20 min after birth, the lung ultrasound score for neonates requiring respiratory support at the NICU was highly predictive. (Blank *et al.*, 2017) In the ULTRASURF study, a randomized controlled trial from Rodriguez-Fanjul *et al.* in 2020, NPLUS was performed within 1 hour after birth in preterm neonates (≤ 32 weeks of gestation) with RDS. In the study protocol, three scans of the anterior, lateral, and posterior chest walls were performed on each side. A 0- to 3-point score was given for each scanned area with a total score ranging from 0 to 18. One randomized group received surfactant based on this lung ultrasound score ≥ 8 and FiO₂ thresholds, in the other group surfactant was administered solely based on FiO₂ thresholds. In the group, in which the diagnosis was based on the lung ultrasound score, neonates received earlier surfactant without increasing the number of patients requiring surfactant treatment. (Rodriguez-Fanjul *et al.*, 2020)

Neonates born by a Caesarean section are particularly prone to have an altered adaption to extrauterine life. Especially in the first hours after birth, TTN may occur due to delayed lung fluid clearance after birth. (Riskin *et al.*, 2005; Poerio *et al.*, 2021) While acute RDS in the first hours after

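### Mode of support is binary, but its link with the score is reported only as a correlation coefficient whose attainable size depends on how many infants are ventilated invasively; a strong relation could read as weak if they are few

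*Combined protocol and SAP*

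**What the plan says.** Hypothesis IV (Section 3) proposes a correlation between the score at 5, 15, 30 and 60 minutes and "the length of respiratory support and the required mode of ventilation". Section 5 serves it with the "correlations between the lung ultrasound score, length of respiratory support and the mode of ventilation", using "either the Spearman's rank correlation coefficient or the Pearson's correlation depending on which one is more appropriate". Section 6 lists the variable among the secondary outcomes as "Mode of respiratory support (non-invasive versus invasive ventilation", that is, as two categories.

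Nothing else in Section 5 relates the score to mode. The ROC analysis covers support beyond 1 hour and NICU admission. The t-test, Mann-Whitney, χ² and Fisher comparisons are between infants transferred to the NICU on support and infants off support at 60 minutes.

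The status of the analysis is explicit: "The correlation analyses are considered in an explorative sense; therefore, no multiple testing corrections will be performed". The documents give neither an expected number of invasively ventilated infants nor a scale for calling a coefficient weak or strong.

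**The concern.** A correlation coefficient is normally read on a scale where 1 is a perfect relation. When one variable has two categories and the other has many distinct values, Spearman's coefficient cannot reach 1, and the most it can reach falls as the smaller category shrinks. Two studies in which the score separates the modes equally well would report different coefficients merely because they ventilated different proportions invasively.

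The size of the estimate is what is at stake. The coefficient is the only planned summary for the mode part of Hypothesis IV. It would stand beside a coefficient for length of support in minutes, which is not limited in this way, and a reader would naturally compare the two. In a pilot meant to inform a later study, an estimate of association should be readable without knowing the group split.

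**Working it through.** **Inputs**
- Sample size n = 40, from Section 4: "Statistical analysis for cut-off determination will be performed with a sample-size of 40 individuals". The groups are described as "comparing 20 neonates who are transferred to the NICU with 20 neonates who initially need respiratory support but then do not require any" at 60 minutes.
- Score scale, from Section 2: "A 0- to 3-point score was given for each scanned area with a total score ranging from 0 to 18". It has 19 possible values. Section 4 adopts this score.
- Number ventilated invasively, k: not in the documents. Assumed range 1 to 20 of 40.

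The plan states no correlation or power figure, so there is none to reproduce.

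**Step 1. Spearman under perfect separation, score without ties.** Every invasive infant scores above every other infant:

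rho_max = √[3k(n − k)/(n² − 1)], with n² − 1 = 1,599.

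| k | 3k(40 − k) | rho_max | AUC |
|---|---|---|---|
| 1 | 117 | 0.27 | 1.0 |
| 2 | 228 | 0.38 | 1.0 |
| 4 | 432 | 0.52 | 1.0 |
| 6 | 612 | 0.62 | 1.0 |
| 8 | 768 | 0.69 | 1.0 |
| 10 | 900 | 0.75 | 1.0 |
| 20 | 1,200 | 0.87 | 1.0 |

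Direct calculation of rho with mid-ranks gives the same values. Section 5 does not say which infants enter the analysis. If only the 20 NICU infants do, the values are 0.38 (k = 1), 0.52 (k = 2), 0.69 (k = 4) and 0.87 (k = 10).

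**Step 2. Imperfect separation.** Without ties, rho = (2·AUC − 1) × rho_max. For an assumed AUC of 0.75, rho is 0.5 × 0.378 = 0.19 with 2 invasive cases and 0.5 × 0.750 = 0.38 with 10. The relation is the same and the coefficient doubles.

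**Step 3. Ties.** With simulated scores rounded to 0–18 (assumed mean/SD 4/2, 6/3 and 9/4), the ceiling hardly moves: for k = 2 the median is about 0.38 and the maximum 0.39. Many infants tied at the floor do matter. In an assumed sample of 28 infants at 0, 8 at 1 to 3, and 4 invasive infants at 6 to 9, rho is 0.64 against 0.52 without ties. With 30 at 0, 8 at 1 to 3, and 2 invasive infants at 8 and 9, it is 0.50 against 0.38.

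**Step 4. Pearson.** For a normally shaped, perfectly separated score the coefficient is 0.37 (k = 1), 0.47 (k = 2), 0.59 (k = 4), 0.74 (k = 10) and 0.81 (k = 20). It also depends on shape. With two invasive infants at 17 and 18 and the rest around 4 (SD 2), it is 0.83, while Spearman stays at 0.38. In the two floor-tied samples of Step 3 it exceeds 0.9.

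**Step 5. The test.** By Step 2, rho is a fixed multiple of 2·AUC − 1 once k is fixed, so a permutation test on rho is the exact Mann-Whitney test. Under perfect separation its two-sided p is 2/40 = 0.05 for k = 1 and 2/780 = 0.0026 for k = 2. The usual large-sample p for Spearman is 0.09 and 0.016 in these cases. That gap comes from the approximation at very small counts, not from the ceiling.

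**The case against.** The strongest reply is that the problem is conditional and the consequence small. Much of this stands.

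- A reader might infer that a perfect relation is bound to look weak. The documents do not support that: they give no invasive count, and at 10 of 40 the Spearman ceiling is already 0.75. The described population (late preterm and term infants, often with self-limiting distress, supported by T-piece and face mask) makes a small count plausible, but does not supply a number.
- A reader might treat the Step 1 values as absolute limits, or suppose Pearson must fall well below 1. Steps 3 and 4 show otherwise: floor ties lift Spearman above those values, and a skewed score can bring Pearson close to 1. Falling scores by 60 minutes, as Hypothesis V expects, could produce such ties.
- A reader might infer that unsupported infants have no category for mode. Section 6 lists mode once, not per time point, and both planned groups have received support.
- Hypothesis IV asserts only that a correlation exists and sets no strength, and the documents do not say that this coefficient will be used to size the main study.

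What does not stand is the exploratory label as a full answer. It explains why no multiplicity correction is made; it does not make the estimate interpretable. Pearson's occasional high values do not help either, since its size then depends on the score's shape as well as on the split.

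**Conclusion.** The point holds in a limited form. The only planned measure for score against mode is a coefficient whose attainable size depends on the share ventilated invasively. With a score largely free of ties and 1 to 4 invasive infants among 40, perfect separation gives a Spearman coefficient of 0.27 to 0.52, which could be read as weak or moderate. From about 6 infants the value exceeds 0.6, and the risk of misreading recedes.

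This rests on the assumed range for the invasive count and on few ties at low scores. It concerns the size and comparability of the estimate. It does not invalidate the test for an association, the primary analyses or the correlation with length of support. The improvement is worth making but not critical.

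**What to change.** In Section 5, take mode of support out of the correlation sentence and state for each scan time:

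- the number of infants in each mode category, and which infants are included;
- an exact Mann-Whitney comparison of the score between categories;
- the AUC with a 95% confidence interval from a named method that remains valid when separation is complete, for example a score-type or exact interval. DeLong or Wald intervals should not be used, because they collapse to zero width when the AUC is 1;
- where invasive cases are very few, a listing of their individual scores in addition to the estimate, not in place of it.

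Keep Spearman's correlation for length of support. The analysis stays exploratory.

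The cost is a change of wording. Mann-Whitney and the AUC are already in Section 5, and no further infants or data are needed. The sponsor should check that the software named there provides the chosen interval.
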